### 10.1.2 Phase 1b (Combination) Arm

As each patient completes 1 Treatment Cycle of the Run-In Arm, they will be offered the combination treatment and may commence that combination treatment immediately providing

that there is no residual toxicity > Grade 1 or in the opinion of the Investigator has recovered from any Study-associated toxicity. Each patient will receive the same idronoxil dosage as they received in the Run-In Arm. A Treatment Cycle is 28-days.

Idronoxil treatment will be daily for 7 consecutive days, commencing on Day 1 and continuing until Day 7.

Carboplatin treatment will be administered intravenously on Day 2 of the Treatment Cycle, starting with a carboplatin dosage of AUC=4 for the initial 3 Treatment Cycles, before proceeding to an AUC=6 for up to 3 remaining Treatment Cycles.

The maximum dosage of carboplatin that may be administered per Treatment Cycle is 600 mg (AUC=4) and 900 mg (AUC=6).

Patients can receive up to 6 treatment cycles of combination therapy at the discretion of the Investigator provided that the patient is not experiencing DLT and the patient, in the opinion of the Investigator, is not experiencing disease progression.

DLT during the Combination Arm of the Study will be managed as a result of discussion between the Investigator, the Medical Monitor and the Sponsor and could involve withholding of idronoxil and/or carboplatin until the patient recovers, and/or a reduction in the dosage of idronoxil and/or carboplatin through a change to a lower idronoxil and/or carboplatin dosage.

If DLT recurs on re-introduction of treatment, the future of that patient is to be discussed with the Medical Monitor.

If a second patient develops a DLT within any treatment regimen, then dose escalation will cease and the prior dose level will be declared the MTD for the combination therapy.

### **10.1.3 Phase IIa Arm**

This Arm can be activated where, in the opinion of the Principal Investigators and the Sponsor, sufficiently meaningful clinical responses have occurred in the Phase Ib Arm of the Study to warrant additional patient enrolment.

There will be a maximum of 2 additional cohorts. Each cohort will comprise up to an additional 10-12 patients with a specific form of cancer. The nature of these 2 additional Phase IIa cohorts will be determined by agreement between the Principal Investigators and the Sponsor.

Patients will be treated with a combination of idronoxil and carboplatin using one of the same treatment schedules as used in the Phase Ib Arm of the Study. Which of the 4 idronoxil/carboplatin dosage combinations that forms the Phase Ib Arm dosage matrix to be used in the Phase IIa Arm, is something that will be determined by agreement between the Principal

Investigators and the Sponsor.

Patients will receive treatment for a maximum of 6 Treatment Cycles provided that the patient is not experiencing DLT and the patient, in the opinion of the Investigator, is not experiencing disease progression.

Patients will be followed for safety and tolerability, and will be monitored and assessed by laboratory testing values as outlined in Section 10.2.

#### **10.1.4 Definition and Determination of Dose Limiting Toxicity (DLT) and Maximum Tolerated Dose (MTD).**

The Maximum Tolerated Dose (MTD) of idronoxil as a monotherapy in the Phase Ia Run-In Arm will be defined as the dose level immediately below the dose level at which 2 of the first 4 patients per cohort (or at least 3 of 8 patients) during the first cycle of that particular Treatment Regimen experience DLT (related to therapy). Additional patients will be recruited so that at least 6 patients are treated at the designated MTD, with no more than 1 DLT observed among the 6 patients. The MTD will be defined in terms of NCI-CTC graded toxicity during the patients' treatment cycle (21 days).

A dose limiting toxicity (DLT) will be defined as any one of the following occurring during the first treatment cycle 1:

- NCI-CTCAE  $\geq$  Grade 3 neutropenia lasting  $\geq$  5 days OR febrile neutropenia (fever  $\geq$  38.5°C) Grade 4 thrombocytopenia, or Grade 3 thrombocytopenia associated with bleeding;
- NCI-CTCAE  $\geq$  Grade 3 abnormal laboratory values (except neutropenia and thrombocytopenia) that are assessed as clinically significant and causally associated with NOX66;
- NCI-CTCAE  $\geq$  Grade 3 non-laboratory toxicity that is assessed as causally associated with NOX66; (excluding alopecia, rash, nausea, diarrhea, and vomiting if controlled with standard supportive therapy);

Once any DLT is reported, at least two more patients will be enrolled at the same dose level. Escalation will continue only if a DLT is limited to one of 4 patients. If a DLT occurs in 2 or more patients, further dose escalation will cease and the MTD will be the next lower level.

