### 7.1 Phase I Arm

In the **Phase Ia (Run-In) Arm**, patients will self-administer idronoxil rectally either once or twice (12-hourly) daily for 14 consecutive days for one (21-day) Treatment Cycle using one of 2 idronoxil dosages.

The main purpose of the Phase Ia Arm is to confirm the tolerability of idronoxil (in the NOX66 dosage formulation) when used as a monotherapy over an extended period of treatment (14 consecutive days).

The **Phase Ib (Combination) Arm** will commence immediately following the Phase Ia (Run-In) Arm and will comprise idronoxil being administered in combination with carboplatin. Patients will remain in the same two starting cohorts and remain on the same idronoxil dosage.

Within each 28-day combination treatment cycle, idronoxil treatment will commence on Day 1 and continue daily for 7 consecutive days; carboplatin will be administered intravenously on Day 2.

There will be two different dosages of carboplatin administered: AUC = 4 and AUC = 6. Patients will start with the lower dose and receive that for 3 Treatment Cycles. Providing there is no DLT, patients then will progress onto the higher dosage of carboplatin which they will receive for up to a further 3 Treatment Cycles.

The primary aim of this phase is to see if idronoxil can induce a meaningful clinical response (complete or partial remission by RECIST) in combination with carboplatin in cancers that have stopped responding to standard chemotherapy and generally would be considered unlikely to respond to further standard therapy. And then further, to see if this meaningful combination anti-cancer effect is possible with a dosage of carboplatin that would be regarded generally as being well tolerated but unlikely to deliver a significant anti-cancer effect.

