#### **8.5 PATIENT REPLACEMENT**

Patients who cannot be evaluated as part of the efficacy analysis may be replaced in the study up to total of 16 evaluable patients.

Replacement will occur at end of all safety cohort assessments and patient may be enrolled at the highest tolerated dose level, commencing with treatment cycle 1 of Phase 1b.

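### The DLT definition covers only the first treatment cycle, yet the protocol acts on DLTs at the step to carboplatin AUC 6 and through Cycle 6; the SAP lists no DLT table

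*Protocol*

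**What the plan says.** Protocol 10.1.4 opens with the MTD of idronoxil as monotherapy in the Phase Ia run-in, judged over a 21-day cycle. It then gives the protocol's single DLT definition: "A dose limiting toxicity (DLT) will be defined as any one of the following occurring during the first treatment cycle 1". It does not say whether this means the run-in or the combination arm, and no separate combination definition exists.

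Other sections use DLTs well beyond one cycle:

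- Section 7.1, on the step after three cycles at AUC 4: "Providing there is no DLT, patients then will progress onto the higher dosage of carboplatin".
- Section 10.1.2, on management: "DLT during the Combination Arm of the Study will be managed as a result of discussion" between the Investigator, the Medical Monitor and the Sponsor. It also allows up to six combination cycles only while the patient is free of DLT.
- Section 10.1.2, on the combination MTD: "If a second patient develops a DLT within any treatment regimen, then dose escalation will cease and the prior dose level" becomes the MTD for the combination.
- Section 10.1.3, on Phase IIa: "Patients will receive treatment for a maximum of 6 Treatment Cycles provided that the patient is not experiencing DLT".

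Protocol 13.2 promises the number and percentage of patients with DLTs by dose cohort, by DLT and by system organ class. SAP 8.2 and the table listing in SAP Section 11 name no such output.

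**The concern.** DLTs and the MTD in combination with carboplatin are part of the first primary objective (6.1), and 13.1 says the study is to guide the dose combination taken into later trials. If the definition closes after one cycle, the rules that rely on it have little or nothing to act on. The AUC 6 cycles, where carboplatin exposure is highest, could not contribute a single DLT. Two readers could then report different DLT counts, and different combination MTDs, from the same data. With no DLT table in the SAP, nothing in the analysis plan would force the question to be settled before reporting.

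**Working it through.** The plan gives no DLT rate or operating characteristic to reproduce; 13.1 simply judges 8 patients per combination adequate. The check is a comparison of texts, followed by a count of days.

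**1. Rules against the window**

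| Rule | Combination cycles it concerns | Inside a one-cycle window |
|---|---|---|
| 7.1, step to AUC 6 | 1-3 | Cycle 1 at most |
| 10.1.2, continuation | 1-6 | Cycle 1 at most |
| 10.1.2, two-patient rule and MTD | AUC 4 (1-3) and AUC 6 (4-6) | Cycle 1 at most; no AUC 6 cycle |
| 10.1.3, Phase IIa continuation | 1-6 | Cycle 1 at most |

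**2. What cycle 1 could mean**

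- *The run-in.* The preceding MTD text is about Phase Ia and 21 days. On this reading, replacement patients, who enter "commencing with treatment cycle 1 of Phase 1b" (8.5), have no DLT window at all.
- *The first combination cycle.* The same words in 8.5 show that the protocol also numbers combination cycles from 1.
- *The first cycle of each carboplatin level (Cycles 1 and 4).* This needs a phrase borrowed from the monotherapy MTD sentence, "during the first cycle of that particular Treatment Regimen experience DLT (related to therapy"), which is confined to Phase Ia.

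**3. Share of planned combination time covered**

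Total 6 x 28 = 168 days; 3 x 28 = 84 days at each AUC.

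| Reading | All days | AUC 4 days | AUC 6 days |
|---|---|---|---|
| Run-in | 0/168 = 0% | 0/84 | 0/84 |
| First combination cycle | 28/168 = 16.7% | 28/84 | 0/84 |
| Cycles 1 and 4 | 56/168 = 33.3% | 28/84 | 28/84 |

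Even the widest reading leaves 168 - 56 = 112 days (66.7%) uncounted. These are planned days. Continuation beyond Cycle 6, which the synopsis allows, would lower the shares.

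**4. A concrete case**

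Grade 4 thrombocytopenia meets the criteria in 10.1.4. In Cycle 3 at AUC 4 it falls outside all three windows, so the condition in 7.1 is met and the patient may step up. In Cycle 5 at AUC 6 it again falls outside all three, so it does not count towards the two-patient rule.

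**5. How the window affects the two-patient rule (illustration only)**

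Let q be an assumed DLT risk per cycle, k the number of cycles counted, and n the patients in one combination. Then p = 1 - (1 - q)^k and P(at least 2) = 1 - (1 - p)^n - n p (1 - p)^(n-1).

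For n = 8 and q = 0.10:
- k = 1: p = 0.10, so 1 - 0.9^8 - 8(0.10)(0.9^7) = 0.187.
- k = 3: p = 0.271, so 1 - 0.729^8 - 8(0.271)(0.729^7) = 0.683.

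| Assumed q | n = 8, one cycle | n = 8, three cycles | n = 5, one cycle | n = 5, three cycles |
|---|---|---|---|---|
| 5% | 0.057 | 0.319 | 0.023 | 0.151 |
| 10% | 0.187 | 0.683 | 0.081 | 0.411 |
| 15% | 0.343 | 0.878 | 0.165 | 0.638 |

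The rates, n = 5, constant independent risk and full retention are assumptions. The table shows only that the window cannot be changed without looking at the threshold.

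**6. SAP output**

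SAP 8.2 tabulates adverse events for the run-in, AUC 4 and AUC 6, with severity and relationship. That does not identify DLTs, which also depend on neutropenia lasting at least 5 days, bleeding, clinical significance and control by supportive care.

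**The case against.** The strongest reply is that nobody would apply 10.1.4 in isolation. Section 10.1.2 speaks of DLTs during the combination arm and of their recurrence on re-introduction of treatment, so the authors plainly meant to reuse the toxicity criteria there. That is right about intent. It does not rescue the text: 10.1.4 is the only definition, and nothing says which combination cycles count, least of all for the two-patient rule.

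A reader might go further and infer the following, which the documents do not support:

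- *Patients at AUC 6 are unprotected.* Section 9.4 restricts re-treatment after Grade 3 or worse events related to idronoxil, 10.1.2 provides for withholding or reducing either drug, the Medical Monitor reviews toxicity (14.2), and SAP Section 9 provides periodic DLT review.
- *Attribution to NOX66 is a defect in the combination arm*, because one criterion reads "non-laboratory toxicity that is assessed as causally associated with NOX66". The objective concerns DLTs of idronoxil. The neutropenia and thrombocytopenia criterion carries no causality condition, and the Possible category in Table 12 admits events that another drug could also explain.
- *The prior dose level cannot be worked out.* The lowest combination has no lower level in any escalation. For 800 mg with AUC 6 the natural step back is 800 mg with AUC 4, since idronoxil is fixed within a patient. What remains is loose terminology: regimen means the idronoxil cohort in Table 2 and the carboplatin dose in the synopsis, although 10.1.3 and 13.1 point to the combination.
- *The SAP has withdrawn the DLT summary.* Protocol 13.2 still requires it, and the list in SAP 8.2 need not be exhaustive. It is a missing output, not missing data. SAP 2.2 omits the no-DLT condition, but it is background and governs no dosing.

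The closing paragraph of 10.1.4 also stops escalation at two DLTs and is not expressly limited to the run-in. It relies on the same definition, so it has the same gap.

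**Conclusion.** The concern holds: the stated window contradicts the rules that depend on it. Taken literally, none of the 84 planned AUC 6 days can yield a DLT, and at most 28 of the 84 AUC 4 days can inform the step to AUC 6. Only by borrowing the monotherapy phrase do 28 AUC 6 days come in. This rests on the text and the planned cycle lengths, not on any assumed event rate; the trigger probabilities are not estimates for this trial.

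The consequence is limited. The study is descriptive, MTD is not expected to be reached (10.1.1), the Phase IIa dose is set by agreement (10.1.3), and clinical review continues throughout. What is at risk is the meaning of the combination DLT count and of any declared combination MTD. It should be fixed.

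**What to change.** - **Protocol 10.1.4.** Limit the cycle 1 window to the Phase Ia run-in. State that in the combination arm the same criteria apply in all cycles for the patient-level rules, namely the step to AUC 6 and continuation.
- **Protocol 10.1.2, two-patient rule.** Name the counted window so that it includes AUC 6 cycles. Count by idronoxil/carboplatin combination. For an AUC 6 combination, name the same idronoxil dose at AUC 4 as the prior dose level.
- **SAP 8.2 and Section 11.** Add the DLT table promised in Protocol 13.2, by idronoxil cohort and period (run-in, AUC 4, AUC 6), with patients entering each period as the denominator.

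The cost is wording in two protocol sections and one SAP table, with no extra patients or visits. It is not wholly editorial. A fixed count of two fires more often over a longer window (in the illustration with 8 patients and 10% per cycle, 19% becomes 68%), so the clinical team should confirm or change the threshold. Also, 8.4 lists a DLT under 10.1.4 as a withdrawal criterion; once the definition covers all combination cycles, 8.4 should defer to the dose management in 10.1.2 for that arm.

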## 10.2 CLINICAL AND LABORATORY ASSESSMENTS

### 10.2.1 Demographic and Other

A medical history will be obtained at screening. Medical history will include demographic data (e.g., date of birth, race/ethnicity). In addition, medical information will be recorded, including:

- all medical conditions and disease states that require current or ongoing therapy, and
- other medical conditions and disease states that, in the opinion of the Investigator, are relevant to the patient's study participation.

### 10.2.2 Safety

The safety and tolerability of idronoxil will be assessed by monitoring and evaluation of clinical laboratory investigations as below:

- Physical examination, inclusive of Eastern Cooperative Oncology Group (ECOG) performance status.
- Vital signs including height (screening only), weight, standing and supine blood pressure, resting pulse rate, body temperature and respiratory rate.
- Complete Blood Count (CBC) and Chemistry including: white blood cells with differentials, red blood cells, hemoglobin, hematocrit, mean corpuscular volume (MCV), mean corpuscular hemoglobin (MCH), mean corpuscular hemoglobin concentration (MCHC), platelets, sodium, potassium, calcium, creatinine, total protein, albumin, bilirubin (total, direct), AST/SGOT, ALT/SGPT, alkaline phosphatase (ALP); urinalysis (dipstick). Urine microscopy will be performed if urinalysis values are out of range and the investigator deems that the microscopy is clinically warranted.

Non-fasting samples for clinical laboratory analysis will be collected by a qualified staff member

- 12-lead ECGs will be taken using a serviced and calibrated machine in triplicate, within 5 minutes of each other (over 15 minutes), to calculate the mean QTc value to ensure the patients eligibility for study enrollment. ECGs should be taken after the patient has been resting supine for 5 minutes.
- Blood-based pregnancy tests will be performed on female subjects at Screening and End of Study visit
- Adverse event (AE) monitoring using the National Cancer Institute Common Terminology Criteria for Adverse Events.

Haematology, clinical chemistry and urinalysis will be performed by the site's local accredited laboratories.

### **10.2.3 Pharmacokinetic and Biomarker**

Idronoxil levels will be assayed both in plasma samples and 24-hour urine samples collected from patients in both the Phase Ia and Phase Ib Arms of the Study. See section 10.4.6.

Biomarkers (ceramide, sphingosine kinase and ENOX 2 levels) will be measured in the same plasma samples collected for pharmacokinetic analysis. See section 10.4.7.

Plasma collection and 24-hour urine collection procedures are outlined in APPENDIX B.

Idronoxil and biomarker assays will be undertaken by the Sponsor performed by a designated laboratory.

## **10.3 ASSESSMENT OF DISEASE STATUS**

Disease status will be assessed by standard RECIST criteria and ECOG Score. Objective responses will be recorded and reported.

### **10.3.1 Radiologic Assessments**

Baseline radiology by CT or MRI **with contrast** should be performed as close as possible to the start of treatment, but no longer than 28 days (4 weeks) prior to Cycle 1, Day 1. For the purposes of this study patients should be re-evaluated at the Investigator's discretion, but at a minimum of every 12 weeks. The radiologic images should be performed consistently for the areas of disease involvement taken for the study evaluation. If the patient has achieved an Objective Response, a confirmatory scan will need to be performed 4 weeks after the response has been noted per RECIST criteria.

Only those patients who have measurable disease at baseline, have received at least one Phase Ib cycle (28 days) of therapy, and have had their disease re-evaluated will be evaluable for response. (Note: Patients who exhibit objective disease progression prior to the end of cycle 1 will also be considered evaluable).

### **10.3.2 Assessment of Response in Patients with Measurable Disease**

Assessments of disease response and progression should be made according to the Response Evaluation Criteria in Solid Tumors (RECIST) version 1.1 (Eisenhauer et al., 2009).

## 10.4 STUDY VISITS

### 10.4.1 Screening

The purpose and the procedures of the study will be fully explained to participants at the screening visit by the Principal Investigator and support staff and every patient approached regarding the study will be provided with the Informed Consent Form (ICF). Patients wishing to enroll in the study will sign the ICF prior to initiating any study related investigations or procedures. Radiological scans performed prior to consent can be utilized for the purposes of the study if they have been performed as part of routine clinical practice and the patient consents for their medical records to be reviewed by the Sponsor.

All screened patients who sign the informed consent form (ICF) must be recorded on the Screening/Enrollment Log. If a subject who signs an ICF is not enrolled in the study, please provide the reason for exclusion on the log. The Screening/Enrollment Log will be retained within the Investigator Site File.

The screening visit should occur at least 7 days before the commencement of NOX66 treatment. The following procedures are to be performed at the screening visit:

- Review and sign Informed Consent Form
- Review Inclusion and Exclusion Criteria
- Review and record medical history including previous anti-cancer therapy
- Physical examination
- Determination of ECOG performance status (APPENDIX A)
- Vital signs
- 12-lead ECGs will be taken in triplicate, within 5 minutes of each other (over 15 minutes)
- Complete Blood Count
- Serum  $\beta$ -hCG pregnancy test (if female is of child bearing potential)
- Review and record all concomitant medications
- Tumor imaging (CT or MRI), including area of disease involvement. Note: tumor imaging may be performed anytime within 28 days of Cycle 1 Day 1

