### 8.2 INCLUSION CRITERIA

Patients must fulfill all of the following inclusion criteria to be eligible to enroll into the study:

1. Provision of informed consent.
2. Male or female  $\geq 18$  years of age.
3. Histologic or cytologic confirmed locally advanced or metastatic cancer that has no standard therapeutic alternatives.
4. At least 1 measurable lesion by CT/MRI scan.
5. ECOG Performance status 0-1 (Appendix A).
6. A minimum life expectancy of 12 weeks.
7. Adequate bone marrow, hepatic and renal function as evidenced by:
  - Absolute neutrophil count (ANC)  $> 1.5 \times 10^9/L$
  - Platelet count  $> 100 \times 10^9/L$
  - Hemoglobin  $> 9.0$  g/dL
  - Serum bilirubin  $< 1.5 \times$  ULN
  - AST/ALT (SGOT/SGPT)  $< 2.5 \times$  ULN for the reference laboratory or  $< 5 \times$  ULN in the presence of liver metastases
  - Serum creatinine  $< 1.5 \times$  ULN
8. Female patients who are known to be capable of conception should have a negative serum pregnancy test (beta-human chorionic gonadotropin ( $\beta$ -hCG)) within 1 week of starting the study.
9. All potentially fertile patients will agree to use an effective form of contraception during the study and for 90 days following the last dose of NOX66 (an effective form of contraception is defined as an oral contraceptive or a double barrier method).
10. At least 4 weeks must have elapsed prior to commencement of NOX66 treatment since prior chemotherapy, investigational drug or biologic therapy and any toxicity associated with these treatments has recovered to  $\leq$  NCI-CTCAE Grade 1.

11. At least 21 days must have elapsed prior to Day 1 Cycle 1 since radiotherapy (limited palliative radiation is allowed > 2 weeks), immunotherapy or following major surgery and any surgical incision should be completely healed.

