**Table 4. Schedule of Assessments – SCREENING**

Obtain Informed Consent	X
Review Inclusion/Exclusion Criteria	X
Medical History	X
Physical Examination (PE)	X
12 Lead ECG	X
ECOG Performance Status	X
Vital Signs	X
Clinical laboratory tests	
Complete Blood Count (CBC)	X
Serum chemistry	X
Pregnancy test (if applicable)	X
Urinalysis (dipstick)	X
Concomitant medication review	X
Tumour imaging	X

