8.2 Adverse events

Adverse events will be coded by MedDRA SOC and Preferred Term, summarised and tabulated for the safety population in the monotherapy arm (phase 1a), in combination arm (phase 1b) with low dose (AUC4) carboplatin and with high dose (AUC6) carboplatin and overall treatment. For each preferred term the number and percent of subjects reporting each adverse event will be tabulated by cohort and 'Overall'. These include:

- Adverse event summary table
- Adverse events occurring prior to study commencement
- All adverse events occurring after study commencement
- Most common (>15 %) treatment-emergent adverse events in any cohort
- Treatment emergent adverse events that were possibly, likely or certainly related to the study medication
- Serious adverse events
- Severe adverse events
- Adverse events causing withdrawal
- All adverse events by maximum severity and relationship to study treatment, with subject identification.

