11. TABLE AND FIGURE LISTINGS

Table Section	Table Title (Population)
Section 10.1	Patient disposition (All populations)
	Completion and withdrawal (Safety population)
Section 11.2	Demographics (Safety population)
	Disease history (Safety population)
	Prior medical history events (Safety population)
	Current medical history events (Safety population)
	Prior medications (Safety population)
	Concomitant medications (Safety population)
	New medications (Safety population)
	Prior chemotherapy (Safety population)
	ECOG status (Safety population)
Section 11.3	Compliance (Safety population)
Section 11.4	Tumour measurements (Efficacy population)
	RECIST response rates and durations (Efficacy population)
	Progression-free survival (Efficacy population)
	Overall survival (Efficacy population)
	Plasma concentrations (PK population)
	Pharmacokinetic coefficients (PK population)
Section 12.1	Exposure (Safety population)
Section 12.2	Summary of adverse events (Safety population)
	Pre-treatment adverse events (Safety population)
	Treatment emergent adverse events (Safety population)
	Treatment emergent adverse events considered possibly, probably or definitely related to study treatment (Safety population)
	Severe adverse events (Safety population)
	Adverse events resulting in withdrawal (Safety population)
Section 12.3	Deaths and serious adverse events
Section 12.4	Serum biochemistry (Safety population)
	Biochemistry shift table (Safety population)
	Haematology (Safety population)
	Haematology shift table (Safety population)
	Categorical urinalysis results (Safety population)

Section 12.5	Urinary pH and specific gravity (Safety population)
	Urinary microscopy (Safety population)
	Vital signs (Safety population)
	Physical examination (Safety population)
	ECG parameters (Safety population)
	ECG findings (Safety population)
	Biomarkers (Safety population)

Figure Section	Figure Title (Population)
Section 11.4	Tumour measurements (Efficacy population)
	Pattern of response by cohort (Efficacy population)
	Progression-free survival (Efficacy population)
	Overall survival (Efficacy population)
	Plasma concentrations by cohort (PK population)
Section 12.2	Most common preferred terms (Safety population)
Section 12.5	Biomarkers (for each parameter) (Safety population)

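### The limit on the age of the pregnancy test has no defined anchor, and no pre-dose repeat is scheduled, so following the visit tables can mean first dosing on a test more than a week old

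*Protocol*

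**What the plan says.** Criterion 8 (Protocol 8.2, with the same wording in the synopsis) covers women known to be capable of conception. Their negative serum beta-hCG should fall "within 1 week of starting the study". The lead-in to the list makes the criteria binding at entry: "Patients must fulfill all of the following inclusion criteria to be eligible to enroll into the study".

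The test belongs to the screening visit (Protocol 10.4.1 and Table 4). On the timing of that visit, 10.4.1 says "The screening visit should occur at least 7 days before the commencement of NOX66 treatment". SAP 3.2 repeats the 7-day minimum as a firm requirement and gives its one-day tolerance only to the other visits. Neither document sets a maximum interval for the screening visit.

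On how often the test is done, Protocol 10.2.2 says: "Blood-based pregnancy tests will be performed on female subjects at Screening and End of Study visit". The tables agree. Table 5 (run-in) has no pregnancy-test row, and Tables 6 and 9 mark the test only at End of Study.

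Baseline imaging is treated differently. Protocol 10.3.1 caps its age at "no longer than 28 days (4 weeks) prior to Cycle 1, Day 1".

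**The concern.** One rule sets a maximum age for the test and the other sets a minimum interval for the visit at which it is taken. Both use the same length, one week. Whether they are compatible depends on which event counts as the start of the study, and that is left open. Sites could reasonably apply different limits.

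The test is there to keep a pregnant woman from receiving an investigational drug and then carboplatin. The exclusion of pregnant patients and the contraception rule (criterion 9) lower the risk, but neither detects a pregnancy that begins after the screening sample. The gap is widest for replacement patients. Under Protocol 8.5 they may enter directly at Phase Ib Cycle 1, so the screening test is their only scheduled check before NOX66 on Day 1 and carboplatin on Day 2.

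There is also a compliance side. Protocol 16.3.1 counts enrolment of a patient who does not meet the inclusion criteria as a major violation. A site working only from the visit tables could commit one without noticing.

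**Working it through.** The plan gives no figure to reproduce. The check is an intersection of day windows.

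**Inputs**
- Screening rule: test at least 7 days before first NOX66 (Protocol 10.4.1, SAP 3.2).
- Criterion 8: test at most 7 days before the study starts (Protocol 8.2).
- Time from enrolment to treatment: nominally at most 72 hours, or 3 days (Protocol 11.1). This is advisory; longer delays are to be discussed with the sponsor.

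**Notation.** T is days from the test to first dose and E is days from enrolment to first dose. The screening rule gives T ≥ 7 throughout.

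| Meaning of study start | Criterion 8 becomes | Combined with T ≥ 7 |
|---|---|---|
| First dose | T ≤ 7 | T = 7, that is Day -7 only |
| Enrolment | T − E ≤ 7 | 7 ≤ T ≤ 7 + E |
| Screening | met automatically | T ≥ 7, no maximum |

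For the enrolment reading, E = 0 gives T = 7; E = 1 gives 7 to 8; E = 2 gives 7 to 9; E = 3 gives 7 to 10. A delay beyond 72 hours raises the upper end further. On the first-dose reading, if the one-week limit is taken strictly as T < 7, no day satisfies both rules.

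**Which reading is meant?** The documents point both ways.
- For first dose: SAP 8.2 lists "Adverse events occurring prior to study commencement", and SAP 11 has a table of pre-treatment adverse events. If these are the same output, the SAP equates study commencement with the start of treatment.
- Against: criterion 10 names the start of NOX66 and criterion 11 names Cycle 1 Day 1, so the authors named treatment start when they meant it. Section 8.2 concerns eligibility to enrol, which favours enrolment.

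**Is there a blood draw to use?** Table 5 has Day 1 laboratory tests, and Table 10 has a pre-dose sample that day. Table 9 has a Day 1 blood count and chemistry. In Table 6, the first combination cycle shows no blood draw on Day 1.

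**The case against.** The strongest reply is that sites can comply. Criterion 8 applies whatever the tables list, nothing forbids an unscheduled repeat, and the pregnancy exclusion and contraception rule also apply. The protocol words both criterion 8 and the screening interval as advice, and the SAP's firmer wording is not an instruction to sites. On two of the three readings a scheduled test older than 7 days at first dose can satisfy criterion 8. All of this stands except one part: the lead-in to 8.2 does make criterion 8 binding.

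A reader might go further in three ways that the documents do not support.
- *That the two rules cannot both be met.* A repeat test meets them, and so does screening on Day -7 if one week includes the seventh day.
- *That first dose is clearly the intended anchor.* The SAP headings suggest it, but matching the listing to the table is an inference. An analysis plan does not define a protocol eligibility term, and criteria 10 and 11 point the other way.
- *That most screening days would breach criterion 8.* Such a count would have to borrow the 28-day imaging window for the screening visit, which has no stated maximum. The documents do not say when screening usually takes place.

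What survives is that the schedule omits a test that may be needed, and that the limit meant to trigger it is undefined.

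**Conclusion.** The point holds as a minor patient-safety and compliance correction. On every reading the scheduled test is at least 7 days old at first dose. It is exactly 7 days old if criterion 8 is counted to first dose, nominally up to 10 days if counted to enrolment, and uncapped if counted to screening. The middle figure assumes that treatment starts within 72 hours of enrolment.

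The number of women affected is unknown; only those capable of conception are concerned, and Phase I takes at most 22 patients. A major violation under 16.3.1 arises only if a woman is enrolled without meeting criterion 8. Dosing on an older test does not by itself amount to one. No endpoint, analysis or escalation decision is affected.

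**What to change.** 1. In criterion 8 (Protocol 8.2 and synopsis), keep the screening test for eligibility and replace the undefined start with a named event. Enrolment is suitable because that is when 8.2 applies, and it avoids tying eligibility to a dosing date that may slip.
2. Add one row to the schedules and one sentence to 10.2.2. For women of child-bearing potential whose last test is more than 7 days old, a repeat serum beta-hCG must be negative before the first NOX66 dose. This is a pre-dose safety check, separate from eligibility.
3. In Tables 5 and 9 the repeat can use the existing Day 1 blood draw, provided the result is back before dosing. Replacement patients who enter at Phase Ib Cycle 1 need a separate pre-dose sample, because Table 6 shows no Day 1 draw in that cycle.

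The cost is one changed phrase, one row with its sentence, one extra assay for some women and a possible short wait for the result. With enrolment as the anchor, a woman screened more than a week before enrolment must be retested before she is enrolled. That repeat also serves as the pre-dose check if it is no more than 7 days old at first dose; otherwise a second is needed.
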